2.4.2. Safety Analysis Set

In contrast to the efficacy analysis set, safety analyses will be performed on the safety analysis set, which is defined as all randomized and treated subjects who received at least 1 injection of study agent (partial or complete) according to the actual treatment received during the study, irrespective of the treatment assigned at randomization.

2.4.3. Pharmacokinetics Analysis Set

The PK analysis set is defined as subjects who received at least one injection of guselkumab and have at least one valid blood sample drawn for PK analysis.

2.4.4. Immunogenicity Analysis Set

The immunogenicity analysis set is defined as all subjects who received at least one injection of guselkumab and have at least one appropriate sample collected post guselkumab administration for the detection of antibodies to guselkumab.

In both PK and immunogenicity analyses, subjects will be analyzed according to the treatment they actually receive, regardless of the treatment they are randomized to.

2.5. Definition of Subgroups

To evaluate the consistency of efficacy based on demographic characteristics, baseline disease characteristics, and psoriasis medication history, subgroup analyses will be performed for the primary endpoint, PASI 90, and the major secondary endpoints of PASI 100 and IGA score of cleared (0), all assessed at Week 48. The subgroups for subgroup analyses include the following:

Baseline demographics:

- Sex (male, female)
- Race
- Baseline Age (<45 years, 45 to <65 years, ≥65 years)
- Baseline weight (≤90 kg, >90 kg)
- BMI (Normal [<25], Overweight [25 -<30], Obese [≥30])

Baseline disease characteristics:

- Age at diagnosis (years) (<25, ≥25)
- Psoriasis disease duration (years) (<15, ≥15)
- Baseline PASI (<20, ≥20)
- Baseline IGA (<4, =4)

- Baseline BSA (<20%, ≥20%)
- Psoriatic arthritis (Yes, No)

Psoriasis medication history:

- Phototherapy (ultraviolet B light [UVB] or psoralen and ultraviolet A light therapy [PUVA])
 - Never used
 - Ever used
- Non-biologic systemics (PUVA, MTX, cyclosporine, acitretin, apremilast, or tofacitinib)
 - Never used
 - Ever Used
- Biologics (etanercept, infliximab, alefacept, efalizumab, ustekinumab, briakinumab, ixekizumab, brodalumab, adalimumab, tildrakizumab, or risankizumab)
 - Never used
 - Ever Used
- Non-biologic systemics or biologics (as defined above)
 - Never used
 - Ever used
- Anti-TNF α agent (etanercept, infliximab, adalimumab)
 - Never used
 - Ever used
- IL-12/23 inhibitors (ustekinumab, briakinumab, tildrakizumab, or risankizumab)
 - Never used
 - Ever used
- IL-17 inhibitors (ixekizumab, or brodalumab)
 - Never used
 - Ever used
- Subjects who had an inadequate response to, were intolerant to, or had a contraindication to any of the following four biologic therapies: etanercept, infliximab, adalimumab or ustekinumab

2.6. Statistical Methods**2.6.1. Study Day**

Study Day 1 refers to the first study agent administration date. The study day for an event is defined as:

- Event date - (date of Study Day 1) +1, if event date is \geq date of Day 1
- Event date - date of Day 1, if event date $<$ date of Day 1

2.6.2. Baseline

In general, the baseline measurement is defined as the closest measurement taken prior to or at the time of the first study agent administration date unless otherwise specified.

3. INTERIM ANALYSIS AND DATA MONITORING COMMITTEE REVIEW

No formal interim analysis is planned for this study. There is no Data Monitoring Committee for this study.

4. SUBJECT INFORMATION

Either the full analysis set or the safety analysis set will be used for the subject information analyses as specified below unless otherwise noted. The number of subjects in each analysis set will be summarized by treatment group and overall. In addition, the distribution of subjects by country, and site will be presented.

Simple descriptive statistics, such as mean, median, standard deviation, interquartile range, maximum, and minimum for continuous variables, and counts and percentages for discrete variables will be used to summarize most data and no formal statistical analyses for treatment comparisons will be performed. In addition, subject listings will also be used to present the data.

4.1. Demographics and Baseline Characteristics

4.1.1. Demographics

[Table 2](#) presents a list of the demographic variables that will be summarized by treatment group, and overall for the full analysis set.

Table 2: Demographic Variables

Continuous Variables:	Summary Type
Age (years)	Descriptive statistics (N, mean, standard deviation [SD], median and range [minimum and maximum], and IQ range).
Weight (kg) (<= 90 kg, > 90 kg)	
Height (cm)	
Categorical Variables:	
Age (<45 years, 45 to <65 years, and ≥65 years)	Frequency distribution with the number and percentage of subjects in each category.
Sex (male, female)	
Race ^a (American Indian or Alaska Native, Asian, Black or African American, Native Hawaiian or other Pacific Islander, White, Other, Multiple, Unknown, Not reported)	
Ethnicity (Hispanic or Latino, Not Hispanic or Latino, Not Reported, Unknown)	
BMI (Normal [<25], Overweight [25 -<30], Obese [≥30])	

^a If multiple race categories are indicated, then Race is recorded as “Multiple.”

4.1.2. Baseline Characteristics

Psoriasis baseline disease characteristics (ie, psoriasis disease duration [years], age at diagnosis [years], BSA [%], psoriatic arthritis, baseline IGA score, and baseline PASI score [0-72]) will be summarized by treatment group for the full analysis set.

4.2. Disposition Information

Screened subjects will be summarized overall.

The number of subjects in the following disposition categories will be summarized by treatment group and overall:

- Subjects randomized
- Subjects who received study agent
- Subjects who completed the study
- Subjects who discontinued study agent
- Reasons for discontinuation of study agent
- Subjects who terminated study prematurely
- Reasons for termination of study

The above categories will include summaries over the period of Week 44 (the last study agent administration) and Week 56 if appropriate.

Listings of subjects will be provided for the following categories:

- Subjects who discontinued study agent
- Subjects who terminated study prematurely
- Subjects who were unblinded during the study period
- Subjects who were randomized yet did not receive study agent

4.3. Treatment Compliance

Study agent compliance will be summarized descriptively through Week 44 for the full analysis set. Number of subjects by randomized treatment versus actual treatment will be presented in a summary table.

4.4. Extent of Exposure

The exposure data will be summarized through Week 44. The number and percentage of subjects who receive study agent will be summarized by treatment group for the safety analysis set. Descriptive statistics will be presented for the following parameters:

- Number of administrations
- Cumulative total dose

In addition, the study agent lots received by treatment, including matching placebo for active treatment will be summarized.

4.5. Protocol Deviations

In general, the following list of major protocol deviations may have the potential to impact subjects' rights, safety or well-being, or the integrity and/or result of the clinical trial. Subjects with major protocol deviations will be identified prior to database lock and will be summarized by category by treatment group through Week 56 for the full analysis set.

- Entered but did not satisfy criteria
- Developed withdrawal criteria but not withdrawn
- Received a disallowed concomitant treatment
- Received wrong treatment or incorrect dose
- Other: to be defined in the major protocol deviation criteria document

A listing of subjects with major protocol deviations will also be provided by randomized treatment group.

4.6. Prior and Concomitant Medications

Subjects' prior psoriasis medication history with topical agents, phototherapy, non-biologic systemic therapies, and biologic medications will be summarized by treatment group for the full analysis set. See Section 2.5 for list of medications in each category. In addition, reasons for which subjects discontinued previous systemic therapies including PUVA, methotrexate, cyclosporine, etanercept, infliximab, adalimumab and ustekinumab (contraindication, inadequate response, intolerance [ie, AEs], or other) will be summarized by randomized treatment group for the full analysis set.

The number of subjects who received concomitant treatment with a moisturizer for psoriasis will be summarized by randomized treatment group for the full analysis set.

Listings of subjects who received concomitant corticosteroids for indications other than psoriasis and/or psoriatic arthritis and of subjects who received concomitant prophylactic treatment for latent TB infection will be provided.

5. EFFICACY

In general, efficacy data summaries will be provided by treatment group for the full analysis set.

In order to compare the proportion of subjects responding to the two treatments, the Cochran-Mantel-Haenszel chi-square test stratified by investigator site will be used. To test the noninferiority of guselkumab to secukinumab, a 1-sided ($\alpha=0.025$) Z-test² with Mantel-Haenszel weights adjusted by investigator site after pooling will be used. All statistical testing will be performed 2-sided for superiority and 1-sided for non-inferiority.

Descriptive statistics, such as mean, median, standard deviation, minimum and maximum, interquartile range for continuous variables, and counts and percentages for categorical variables will be used to summarize the data. Graphical data displays and subject listings may also be used to summarize the data.

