1.4. Sample Size Justification

This study is designed to evaluate the efficacy of guselkumab 100 mg vs secukinumab 300 mg. The power and sample size were evaluated for the primary endpoint of PASI 90 at Week 48. In addition, since the response rate for guselkumab for PASI 100 at Week 48 is around 50% where the variability is the highest, the power and sample size were also evaluated for this major secondary endpoint. The assumptions for the sample size and power calculations were based on the data from the guselkumab CNTO1959PSO3001 and CNTO1959PSO3002 and the secukinumab Phase 3 studies (ERASURE and FIXTURE).¹ The assumptions used are as follows:

- The proportion of subjects who achieve a PASI 90 response at Week 48 is 70% to 80% in subjects receiving guselkumab and 60% to 70% for subjects receiving secukinumab.
- The proportion of subjects who achieve a PASI 100 response at Week 48 is 44% to 51% in subjects receiving guselkumab and 35% to 40% for subjects receiving secukinumab.

Approximately 1,040 subjects are planned to be randomized in a 1:1 ratio to either guselkumab 100 mg (n=520) (administered at Weeks 0, 4, 12 and q8w thereafter until Week 44) or secukinumab 300 mg (n=520) (administered at Weeks 0, 1, 2, 3, and 4 and q4w thereafter until Week 44).

Based on the above assumptions, the planned sample size, and a noninferiority margin of 10%, the power to demonstrate the non-inferiority for the primary endpoint of PASI 90 at Week 48 and the major secondary endpoint of PASI 100 at Week 48 will be > 99%.

Table 1 provides the power for detecting a treatment difference (superiority of guselkumab over secukinumab) under varying assumptions at a significance level of 0.05 for the primary endpoint PASI 90 at Week 48 and the major secondary endpoint of PASI 100 at Week 48.

Table 1: Power to Detect a Treatment Effect Based on Different Proportions of Subjects Achieving the Primary Endpoint PASI 90 at Week 48 and the Major Secondary Endpoint PASI 100 at Week 48

Secukinumab 300 mg (n=520)	Primary Endpoint PASI 90 at Week 48	
	Guselkumab 100 mg (n=520)	
60%	70%	92%
	75%	>99%
	75%	94%
65%	80%	>99%
	80%	96%
70%	Selected Major Secondary Endpoint PASI 100 at Week 48	
	44%	84%
	45%	91%
	46%	95%
	49%	83%
40%	50%	90%
	51%	95%

PASI = Psoriasis Area and Severity Index.

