5.1. Analysis Specifications

5.1.1. Level of Significance

All statistical procedures to test superiority hypotheses will be performed at a 2-sided significance level of 0.05 and 1-sided at a significance level of 0.025 for non-inferiority. This study is designed to maintain an overall Type I error of 0.05 or less for the primary analysis and major secondary analyses. Nominal p-values will be reported for other secondary analyses.

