To claim the non-inferiority of guselkumab to secukinumab, a 1-sided ($\alpha=0.025$) Z-test with Mantel-Haenszel (MH) weights adjusting for investigator site² will be used. That is, the lower bound of the 2-sided 95% confidence interval (CI) of $P1 - P2$ must be $\geq -10\%$, where $P1$ and $P2$ are the proportions of subjects achieving a PASI 90 response at Week 48 in the guselkumab 100 mg and the secukinumab 300 mg groups, respectively. The 2-sided 95% CI on the difference between guselkumab 100 mg and the secukinumab 300 mg groups will be calculated adjusting for investigator site after pooling using Mantel-Haenszel weights.² If non-inferiority is not established, no further test will be conducted and Step b will be skipped.

- b. If non-inferiority is established in Step a, the superiority test of guselkumab to secukinumab using the CMH chi-square test stratified by investigator site after pooling will be performed at a significance level of 0.05. The proportion difference between guselkumab 100 mg and the secukinumab 300 mg groups and its 2-sided 95% CI will be provided based on normal approximation with Mantel-Haenszel weights adjusting for investigator site.

If both the non-inferiority test and the superiority test are positive, the major secondary hypotheses comparing the guselkumab group and the secukinumab group will be tested sequentially. Otherwise, all remaining p-values will be considered nominal.

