5.2.5. Sensitivity Analysis

To assess the robustness of the primary endpoint analysis results, the following three sensitivity analyses will be conducted.

Sensitivity Analysis 1

For subjects who have a missing PASI score at Week 48, the score will not be imputed. That is, the analysis will be performed using observed data, after applying treatment failure rules (as defined in Section 5.1.3.2).

Sensitivity Analysis 2

The second sensitivity analysis will be performed by using multiple imputations (MI), after applying treatment failure rules (as defined in Section 5.1.3.2). The intermittent missing PASI scores which include PASI scores at Week 0, Week 4 through Week 48 will be imputed using the Markov Chain Monte Carlo (MCMC) algorithm with 200 imputed data sets and seed = 123 to make the missing data pattern monotone. The PASI 90 responses will then be derived based on the imputed score at or before Week 48. The remaining missing data for the PASI 90 response will be imputed with monotone logistic regression with treatment group, baseline PASI, investigator site and PASI 90 response status starting from Week 4 in the model with one imputed dataset and seed = 789 to fill in the remaining missing items in each of the 200 copies of datasets. If the model fails to converge, investigator site will not be included as an explanatory variable. The proportion difference of PASI 90 response at Week 48 adjusted for investigator site (pooling) using Mantel-Haenszel weight between the guselkumab 100 mg and the secukinumab 300 mg groups and its 95% CI combining multiple datasets will also be provided. In addition, the superiority test of guselkumab to secukinumab combining all the multiple imputation datasets using the CMH chi-square test stratified by investigator site will be performed at a significance level of 0.05.

Sensitivity Analysis 3

A generalized linear model with logit link for binary repeated measurement data will also be performed as a sensitivity analysis to compare the proportion of subjects responding to treatments at Week 48, after applying treatment failure rules (as defined in Section 5.1.3.2). The model will include baseline PASI score, treatment group, investigator site, visit starting from Week 4, the interaction of treatment group and visit, and the interaction of baseline PASI score

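### The deciding comparisons adjust for pooled site only; a pre-specified risk difference that also adjusts for baseline PASI, weight and prior biologic use would use data already collected and could gain some precision

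*SAP*

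**What the plan says.** SAP section 5 sets the superiority test for response proportions: "the Cochran-Mantel-Haenszel chi-square test stratified by investigator site will be used". SAP section 5.2.3 computes the non-inferiority interval for the risk difference "adjusting for investigator site after pooling using Mantel-Haenszel weights", and SAP section 5.3.2 carries the same methods to the major secondary endpoints. Protocol section 11 fixes both methods. Site is also the only randomization stratum (Protocol section 5, SAP section 1.5.1), and sites are pooled to at least 10 subjects (SAP section 2.3).

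The three covariates appear elsewhere in the plan:

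- **Baseline PASI** is in the imputation model of Sensitivity Analysis 2. It is also in the outcome model of Sensitivity Analysis 3: "The model will include baseline PASI score, treatment group, investigator site, visit starting from Week 4" (SAP section 5.2.5).
- **Baseline weight and prior biologic use** (never or ever) appear only as subgroup factors: "subgroup analyses will be performed for the primary endpoint, PASI 90" (SAP section 2.5). The subgroup intervals are not adjusted even for site (SAP section 5.2.6).

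Weight is measured at Week 0 (Protocol Time and Events Schedule), and prior biologic use is recorded and summarized (SAP section 4.6). Neither document explains why the deciding analysis stops at site.

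**The concern.** A baseline variable that predicts response can shorten the interval for a risk difference without changing what is estimated. All three variables will be in the database, so using them needs no extra subjects or procedures. The margin, alpha and test order can stay as they are.

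Any gain would matter most where the plan has least reserve. Table 1 gives 83% and 84% power for PASI 100 superiority in the two smallest-gap cells. That test sits fourth among the major secondary endpoints in a fixed sequence, so failing it ends formal testing of the IGA endpoints behind it (SAP section 5.1.1.1).

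**Working it through.** **Inputs from the documents.** There are 520 subjects per arm. Superiority tests are "performed at a 2-sided significance level of 0.05 and 1-sided at a significance level of 0.025 for non-inferiority". For PASI 90, SAP section 1.4 takes a guselkumab rate between 70% and 80%; for the comparator it takes "60% to 70% for subjects receiving secukinumab". For PASI 100, the smallest-gap cells of Table 1 are 35% v 44% and 40% v 49%. The margin is 10 points.

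**Input not in the documents.** R² is the share of outcome variance that the three covariates explain beyond site. It is assumed to be 2% to 10%.

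**Step 1: reproduce Table 1.** Power = Φ[(Δ − 1.96·SE₀)/SE₁], with SE₀ = √(2·p̄(1−p̄)/n) and SE₁ = √([p₁(1−p₁) + p₂(1−p₂)]/n).

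- PASI 90, 60% v 70%: SE₀ = √(0.455/520) = 0.02958 and SE₁ = √(0.450/520) = 0.02942. Then (0.10 − 0.05798)/0.02942 = 1.43, so power is 92.3% (stated 92%).
- PASI 100, 40% v 49%: SE₀ = √(0.49395/520) = 0.03082 and SE₁ = √(0.4899/520) = 0.03069. Then (0.09 − 0.06041)/0.03069 = 0.964, so power is 83.3% (stated 83%).

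The other cells also agree to within 1 point. Table 1 assumes no covariates and is correct as it stands.

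**Step 2: apply the assumed gain.** Replace n by 520/(1 − R²). This gives 531 per arm at 2%, 547 at 5% and 578 at 10%.

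| Scenario | Planned | R² = 2% | R² = 5% | R² = 10% |
|---|---|---|---|---|
| PASI 90, 60 v 70 | 92.3% | 92.8% | 93.5% | 94.7% |
| PASI 90, 65 v 75 | 94.2% | 94.6% | 95.2% | 96.1% |
| PASI 90, 70 v 80 | 96.2% | 96.5% | 97.0% | 97.6% |
| PASI 100, 35 v 44 | 84.4% | 85.2% | 86.2% | 88.0% |
| PASI 100, 40 v 49 | 83.3% | 84.0% | 85.1% | 86.9% |

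The 95% interval half-width at 60% v 70% goes from 5.77 points to 5.71 (R² = 2%) or 5.47 (R² = 10%).

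**Step 3: primary non-inferiority.** At 60% v 70%, (0.10 + 0.10)/0.02942 − 1.96 = 4.84. Power is already above 99%, as stated, so there is nothing material to gain.

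**Step 4: simulation check.** The site-stratified Mantel-Haenszel difference was compared with a logistic model standardized to a risk difference. With covariate R² of about 4.5%, the standard error fell from 2.80 to 2.70 points; with about 8%, from 2.75 to 2.58. The direction agrees with step 2.

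**Step 5: could the covariates simply become further CMH strata?** Assume 70 pooled sites of 15 or 74 of 14 (Attachment 1 is broken in the text version), and splits of 50/50, 50/50 and 30/70 for PASI, weight and prior biologic use. Then 52-55% of non-empty strata hold one arm only, and 58-60% of the information is kept. Power at 65% v 75% falls from 94.2% to about 77-78% before any gain from the covariates. The adjustment has to come from a model, not from more strata.

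**The case against.** The case for leaving the plan alone is substantial.

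- **The analysis matches the design.** Site is the only randomization stratum. A reader might infer from the omission that the primary result is biased, that type I error is affected or that the study is underpowered. The documents support none of these. This part of the objection stands in full.
- **The size is assumed.** PASI 90 is already a percent change from the subject's own baseline, which may weaken baseline PASI as a predictor. Only variance beyond geographically pooled site counts. Missing data and treatment failures count as non-response, which the covariates may not predict. All of this stands: the true gain could lie at or below the low end.
- **The SAP does not call the factors prognostic.** SAP section 2.5 lists them to examine consistency of effect. Baseline PASI in Sensitivity Analysis 3 suggests that it was thought relevant but gives no strength. This stands.
- **An adjusted difference already exists.** Sensitivity Analysis 3 reports a Week 48 proportion difference with an interval from a model containing baseline PASI, so it would be wrong to say that the plan ignores baseline PASI. This stands in part. That analysis omits weight and prior biologic use, leaves missing scores unimputed, and may drop site if the model does not converge. SAP section 5.3.2 extends only Sensitivity Analyses 1 and 2 to the major secondary endpoints.
- **The change is neither free nor risk-free.** CMH is fixed in the protocol, and SAP Amendment 1 was written after enrollment was complete. A logistic model with many small sites can also fail: at a 75% response rate, a 10-subject site has a 0.75¹⁰ = 5.6% chance that every subject responds. This argues for a linear model and for the supportive role as the minimum.

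**Conclusion.** The point holds as a worthwhile, optional efficiency improvement. The deciding test and interval for the primary and major secondary endpoints use pooled site alone, and three collected baseline variables are left out.

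Under an assumed R² of 2% to 10% beyond site, power rises by 0.5 to 2.4 points for PASI 90 at 60% v 70%, and by 0.7 to 3.6 points for PASI 100 at 40% v 49%, on unrounded values. The gain for primary non-inferiority under the planned rates is negligible. The R² range is not in the documents, so these figures show what could be gained, not what is known to be lost.

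A reader might go further and conclude that the planned primary analysis is deficient and must be replaced. The documents do not support that: the analysis is valid, it matches the randomization, and its stated power is correct.

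**What to change.** Before unblinding, pre-specify one adjusted risk difference for the primary endpoint and each major secondary endpoint:

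- **Model:** a linear model for the binary response with robust standard errors, containing treatment, pooled site, baseline PASI, baseline weight and prior biologic use (yes/no). It needs no iterative fit, so no convergence fallback.
- **Data rules:** the same full analysis set, treatment failure rules and non-responder imputation as the primary analysis. Name the robust variance estimator, and give a rule for a missing baseline covariate so that no randomized subject drops out.
- **Decision elements:** the same −10-point margin, alpha and test order. Do not add the covariates as CMH strata.

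At minimum, make this a named key supportive analysis beside the site-stratified CMH and Mantel-Haenszel decision rule. That needs an SAP change only. Making it the decision rule also needs a formal protocol amendment (Protocol section 17.1), because Protocol section 11 fixes the current method; the site-only result would then become supportive.

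The cost is modest programming and a slightly less familiar estimate. No new data are needed.
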